In our previous retrospective study, we evaluated the incidence of occult CNS localization and the impact of such localization on the prognosis of adult patients with ALS at onset. We collected data, between 2007 and 2017, from 240 patients, 103 women and 137 men, median age 44 years (range 17-80). One hundred eighty-four patients (77%) had a B phenotype. Patients were treated according to GIMEMA/NILG protocols or according to the Hyper-CVAD program. One hundred and eight

Version no. 1 dated 1.04.2020

categories of patients were distinguished: patients with overt CNS localization(CC+FCM+), patients with occult CNS localization (CC-FCM+), and patients with absence of disease in the CNS (SNCneg, CC-FCM-). Overall 179 (75%) patients were SNCneg, 43 (18%) had occult CNS localization and finally 18 (7%) had manifest disease. No cases of morphological positivity and cytofluorimetric negativity were observed. Patients with occult or manifest CNS localization presented higher recurrence rates (systemic and meningeal) than SNCneg patients. In addition, disease-free survival and three-year overall survival were significantly longer in patients with no CNS disease than in patients with occult or manifest CNS localization. On the other hand, no significant differences in survivals were observed between patients with occult or manifest CNS localization, confirming that even a small proportion of leukemic cells at this level can influence patients' prognosis. In multivariate analysis, status at diagnosis of occult or manifest CNS localization and age over 45 years were found to be independently associated with shorter overall survival. In conclusion, our study suggests that in adult patients with LLA, FCM allows detection of occult CNS localization, especially under conditions of leukemic cell scarcity in the CRL, and that the presence of such localization appears to be associated with poor prognosis.

However, given the heterogeneity of the treatments our patients had received and the long observation period, a prospective validation study is needed to confirm these data.

The need for further studies is confirmed by the fact that current international guidelines¹¹⁻¹³ do not recommend the use of FCM in the assessment of CSF at onset in adult ALS patients. In addition to confirming the need to perform FCM of CSF at onset to identify patients at higher risk of recurrence, large-scale prospective studies will help to clarify whether or not patients with occult CNS localization should undergo CNS-directed therapy. Understanding this seems particularly important nowadays considering that with the introduction of new drugs (monoclonal antibodies, next-generation tyrosine kinase inhibitors, CAR-T) the therapeutic approach of patients with ALS is increasingly "chemo-free"

Clinical trial proposal and objectives

In light of this, we propose a multicenter prospective study to evaluate the incidence of occult CNS localization and the impact of such localization on clinical outcome.

2.0 Experimental design

Adult ALS patients routinely undergo diagnostic lumbar puncture (PL); CSF samples will be studied by investigation of CC and FCM at the time of the first and subsequent diagnostic PLs.

3.1 Objectives

3.1.1 Primary objective.

To assess the incidence of occult CNS localization in adult patients with ALL.

3.1.2 Secondary objectives

a. To examine associations between occult CNS localization and:

b1 overall survival (OS)

b2 recurrence-free survival (DFS)

b3 overall and medullary or extramedullary recurrence rates

b4 cumulative incidence of recurrence (CIR)

b. To evaluate the correlation between occult CNS localization and minimum residual disease (MRD) levels.

c. Determine the status of CNS occult localization also by molecular biology, comparing the results with those of FCM.

4.0 Study population.

Version no. 1 dated 1.04.2020

4.1 Sample size and duration of the study.

4.1.1.

All patients with Acute Lymphoblastic Leukemia (ALL) who underwent diagnostic lumbar puncture (PL) in the planned 12 months of enrollment will be included in the study. The sample size was calculated to assess the incidence of occult CNS localization; based on clinical experience¹⁴ in order to observe an incidence at diagnosis of 20%, with a 95% confidence interval (two-tailed test) and a width of 0.20, a number of 70 subjects was calculated as the minimum sample size¹⁵. Calculations were performed using PASS software.

4.1.2

The duration of the study will be 12 months of enrollment of the first patient and 24 months of follow-up.

4.2 Patient selection.

4.2.1 Inclusion criteria.

- Patients aged ≥ 18 years with diagnosis of ALL at onset undergoing diagnostic-therapeutic PL.
- Signed written informed consent in accordance with ICH/EU/GCP guidelines and national and local laws.

4.2.2 Exclusion criteria.

- Patients < 18 years of age
- Diagnosis other than ALL
- Inability to perform PL

5.0 Materials and methods

5.1. Methods

5.1.1 CC

Physical chemical examination and cell count and morphological examination will be performed for each CSF sample as per common clinical practice. Morphological examination of the CSF will be performed by preparation of cytocentrifugate (CC) stained with May-Grunwald-Giemsa. Manifest CNS localization will be defined in the unequivocal presence of leukemic cells in the CSF and/or a mononuclear cell count $\geq 5/\text{cml}$.

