5.1.2 FCM

For the FCM examination, which is also performed as part of common clinical practice, CSF samples of sufficient volume will have to be taken via PL. The CSF sample to be stored on ice will be processed within 1 hour of collection to avoid cell deterioration or a specific fixative (TransFix/ethylenediaminetetraacetic acid EDTA; Immunostep SL Salamanca, Spain) should be used. The CSF sample will be concentrated by centrifuging it at 300 g for 4 min. The supernatant will be gently aspirated and the pellet resuspended in PBS+BSA 0.2% in varying amounts depending on the number of tubes to be prepared (100 μl /tube). One hundred μl of the suspension will be incubated with monoclonal antibody mix of interest for 20 min in the dark. A wash with 2 ml PBS+BSA 0.2% will then be performed, centrifuge at 300 g for 3 min. The pellet will be resuspended in 700 μl of PBS+BSA 0.2%. The phenotypic study will be performed using a panel of 6-8 monoclonal antibodies. The antibody panel will include: CD20-FITC, CD10-PE, CD34-PE, CD19-PerCP, CD45-APC, (Becton Dickinson, Mountain View, CA), for line B; CD3-FITC, CD2-FITC, CD7-PE, CD5-APC, CD8-PE, CD4-FITC, CD45-PerCP (Becton Dickinson, Mountain View, CA) for line T. All samples will be acquired until depletion to obtain the highest number of events. FCM positivity will be defined in the presence of ≥ 10 cluster-forming events and leukemic phenotype. FCM acquisition will be done locally, but 3 independent, experienced operators will review each case.

Version no. 1 dated 1.04.2020

5.1.3 Ancillary study. Molecular biology.

Version no. 1 dated 1.04.2020

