Cases will be documented using data collection sheets. A sequential identification number will be assigned to each patient registered in the study. This number will identify the patient and will be included in the data collection sheet thus allowing the patient's anonymity to be maintained. Variables collected will be age, gender, date of ALS diagnosis, immunophenotype at onset, genetic and cytogenetic features of ALS, stratification by risk group, extramedullary localizations, type of chemotherapy, date of first PL, white blood cells at onset and at the time of PL, lactic dehydrogenase levels at onset and at the time of PL, CRL cell count, CRL protein count, CRL cytopsin outcome, date of complete remission. Subsequent data collection sheets will be provided for patient follow-up, at 12 and 24 months after enrollment, in which the number of PLs performed, MMR evaluation, MMR assessment, outcome, date of any recurrence, any SNC radiotherapy, salvage chemotherapy, date of last follow-up, date of death will be reported.

5.3 Statistical considerations.

Patient characteristics will be described by frequency tables for qualitative variables and position indicators for quantitative variables. Associations of clinical-biological parameters with CNS location will be analyzed by Chi-square or Fisher's exact test for qualitative variables and Wilcoxon or Kruskal-Wallis test for quantitative variables. OS will be calculated from the date of treatment initiation to the date of death from any cause; subjects alive at the last follow-up will be censored. DFS will be calculated from the date of achieving complete remission to the date of relapse or death from any cause; subjects alive without progression at last follow-up will be censored. CIR will be estimated via nonparametric method considering death as competitive risk. OS and DFS probabilities will be estimated by Kaplan Meier method; log rank test will be used to compare subgroups. Confidence intervals will be calculated at 95%, all tests will be two-tailed, and differences with $p < 0.05$ will be considered statistically significant. R software (A language and environment for statistical computing. R Foundation for Statistical Computing, Vienna, Austria. URL <https://www.R-project.org/>).

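### Does the primary endpoint lack a usable definition of occult CNS disease, given that a cell count alone can make a patient manifest?

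*Combined protocol and SAP*

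**What the plan says.** Section 3.1.1 sets the primary objective: "To assess the incidence of occult CNS localization in adult patients with ALL". Section 4.1.1 sizes the study "in order to observe an incidence at diagnosis of 20" per cent, with a two-sided 95% confidence interval of total width 0.20, and arrives at 70 subjects.

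Two sections give the building blocks for classifying patients:

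- Section 5.1.1, on cytology (CC): "Manifest CNS localization will be defined in the unequivocal presence of leukemic cells in the CSF and/or a mononuclear cell count" of at least 5. The joining words are and/or, so the count is sufficient alone.
- Section 5.1.2, on flow cytometry (FCM): "FCM positivity will be defined in the presence of ≥ 10 cluster-forming events and leukemic phenotype".

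Neither goes on to say which patients are occult. The explicit labels are in the background account of the earlier retrospective study. Overt disease is CC+FCM+, followed by "patients with occult CNS localization (CC-FCM+), and patients with absence of disease in the CNS (SNCneg, CC-FCM" (the last label is CC-FCM-). The same account adds: "No cases of morphological positivity and cytofluorimetric negativity were observed".

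On timing, section 2.0 says: "CSF samples will be studied by investigation of CC and FCM at the time of the first and subsequent diagnostic PLs". In section 5.2 the data sheet includes "CRL cell count, CRL protein count, CRL cytopsin outcome, date of complete remission". It does not name a CSF FCM result.

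**The concern.** The class is the primary numerator. It is also the exposure in the secondary analyses of OS, DFS, recurrence, cumulative incidence of recurrence and MRD. If two analysts could both follow the document and count different patients as occult, the headline figure would depend on a choice that could be made after the data were seen.

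Setting section 5.1.1 beside the background labels, and reading CC there as morphology alone, three kinds of patient seem to be placed inconsistently:

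- (a) morphology negative, FCM positive, count at least 5: occult by the background labels, manifest by section 5.1.1;
- (b) morphology negative, FCM negative, count at least 5: CNS-negative by the labels, manifest by section 5.1.1;
- (c) morphology positive, FCM negative: manifest by section 5.1.1, with no label in the background.

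Testing at later punctures also seems to leave the time point open, and the data sheet seems to omit the one result that any version of occult requires.

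**Working it through.** **1. Does the current-study text classify everyone?** Let M be leukemic cells on morphology, C a mononuclear count of at least 5, and F FCM positivity under section 5.1.2. Section 5.1.1 gives manifest = M or C. Take occult as F without manifest disease, and negative as neither.

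| M | F | C | Sections 5.1.1 and 5.1.2 | Background labels, CC read as morphology |
|---|---|---|---|---|
| + | + | either | manifest | overt |
| + | − | either | manifest | no label (c) |
| − | + | + | manifest | occult (a) |
| − | + | − | occult | occult |
| − | − | + | manifest | negative (b) |
| − | − | − | negative | negative |

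The middle column fills every row once, so no precedence rule is needed. The last column rests on an assumption. The background account, as supplied, breaks off just before the three categories, and it does not show whether a count entered CC positivity in that study. If it did, rows (a) and (b) would agree as well.

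**2. The plan's own figure.** Inputs from section 4.1.1: p = 0.20, 95% two-sided, total width 0.20. The exact (Clopper-Pearson) limits for x of n are the 0.025 quantile of Beta(x, n−x+1) and the 0.975 quantile of Beta(x+1, n−x). The smallest n with width at most 0.20 is 70: 14/70 gives 11.39% to 31.27%, width 0.1989. The stated 70 is reproduced. It depends on the planning incidence, not on the boundary between occult and manifest.

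**3. What the other reading would do to the primary estimate.** Each type (a) patient shifts it by 1/70 = 1.43 points. The documents do not give the share of CC-FCM+ patients with a raised count, so the number moved, k of 14, is an assumption:

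| k moved | Occult | Estimate | Exact 95% CI |
|---|---|---|---|
| 0 | 14/70 | 20.0% | 11.4–31.3% |
| 1 | 13/70 | 18.6% | 10.3–29.7% |
| 2 | 12/70 | 17.1% | 9.2–28.0% |
| 4 | 10/70 | 14.3% | 7.1–24.7% |
| 6 | 8/70 | 11.4% | 5.1–21.3% |
| 7 | 7/70 | 10.0% | 4.1–19.5% |

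Up to k = 6 the shifted estimate stays inside the k = 0 interval (8/70 = 11.43% against a lower limit of 11.39%). At k = 7, half of the CC-FCM+ patients, it falls outside.

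**4. Types (b) and (c).** Both are FCM negative, so neither can be occult on either reading, and the primary numerator is untouched.

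For (b), the earlier study's rates applied to 70 patients give 179/240 × 70 = 52.2 negative, 43/240 × 70 = 12.5 occult and 18/240 × 70 = 5.25 manifest. One or two type (b) patients (an assumption) would leave a negative group of about 52, which is 1/52 = 1.9% or 2/52 = 3.8% of it. They would join a manifest group of about 5, making up 1/6 = 17% or 2/7 = 29% of it.

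For (c), 0 of 240 were seen. The exact upper limit is 1 − 0.025^(1/240) = 1.53%, and 1.53% × 70 = 1.07. That is the expected number at the limit, not a maximum: at that rate the chance of two or more among 70 is about 29%.

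**5. Time point.** Section 4.1.1 speaks of incidence at diagnosis, section 4.2.1 enrols patients at onset, and section 5.2 records the date of the first puncture. These agree on the first puncture. Later samples do not alter that estimate.

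**6. Data capture.** Section 5.1.2 requires three operators to review each FCM case, and secondary objective c compares molecular results with FCM for occult status. The FCM result is central to the study, and its absence by name from a summary list is weak evidence that it goes unrecorded.

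**The case for a change.** The best argument for a change is that the reading in the middle column is inferred. Section 5.1.1 reserves the abbreviation CC for the stained cytocentrifugate, apart from the cell count, and the background speaks of morphological positivity. A reader who carries those labels forward could keep type (a) patients in the occult class. The reading adopted also puts type (b) patients, with no leukemia found by either method, into a manifest group of about five. The present study is meant to validate the earlier result, so comparability with 43/240 matters, and one sentence would cost almost nothing.

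Parts of this stand. No sentence in the supplied text defines occult for this study, and the background does appear to treat CC as morphology. Type (b) could dilute the small manifest group. But a description of how an earlier study grouped its patients does not compete with a rule written for this one. The argument also cannot have it both ways: if it is unknown whether a count entered CC positivity earlier, then the earlier placement of (a) and (b) is unknown too, and no contradiction has been shown. Repeating the incidence and outcome comparisons under a second rule is optional and would rest on an unknown number of affected patients.

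**Conclusion.** No change is needed. This is a missing sentence that analysts would fill sensibly: occult means FCM positive under section 5.1.2 without manifest disease under section 5.1.1, at the first puncture. On that reading the classes are exhaustive and do not overlap, and the primary incidence is sound.

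The conclusion assumes that section 5.1.1 governs this study and that the background labels do not. If they were applied instead, with CC as morphology alone, each affected patient would move the estimate by 1.43 points. The total cannot be worked out from the documents. The minimum of 70 stands at the 20% planning incidence. Stating the class in the analysis report would help readers, but it would not alter what a careful analyst does with the plan as written.

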5.1.2 FCM

For the FCM examination, which is also performed as part of common clinical practice, CSF samples of sufficient volume will have to be taken via PL. The CSF sample to be stored on ice will be processed within 1 hour of collection to avoid cell deterioration or a specific fixative (TransFix/ethylenediaminetetraacetic acid EDTA; Immunostep SL Salamanca, Spain) should be used. The CSF sample will be concentrated by centrifuging it at 300 g for 4 min. The supernatant will be gently aspirated and the pellet resuspended in PBS+BSA 0.2% in varying amounts depending on the number of tubes to be prepared (100 μl /tube). One hundred μl of the suspension will be incubated with monoclonal antibody mix of interest for 20 min in the dark. A wash with 2 ml PBS+BSA 0.2% will then be performed, centrifuge at 300 g for 3 min. The pellet will be resuspended in 700 μl of PBS+BSA 0.2%. The phenotypic study will be performed using a panel of 6-8 monoclonal antibodies. The antibody panel will include: CD20-FITC, CD10-PE, CD34-PE, CD19-PerCP, CD45-APC, (Becton Dickinson, Mountain View, CA), for line B; CD3-FITC, CD2-FITC, CD7-PE, CD5-APC, CD8-PE, CD4-FITC, CD45-PerCP (Becton Dickinson, Mountain View, CA) for line T. All samples will be acquired until depletion to obtain the highest number of events. FCM positivity will be defined in the presence of ≥ 10 cluster-forming events and leukemic phenotype. FCM acquisition will be done locally, but 3 independent, experienced operators will review each case.

Version no. 1 dated 1.04.2020

5.1.3 Ancillary study. Molecular biology.

Version no. 1 dated 1.04.2020

Given the scarce data in the literature regarding the role of molecular diagnostics in the diagnosis of occult localization in the CNS, the study will include an ancillary part to evaluate this role by comparing molecular findings with FCM. The success of the molecular study will be related to the number of leukemic blasts present in the CSF, so a morphological study will be needed on the starting material that will be able to give accurate information about the material being processed. All cases will need to be processed within one hour of collection of the material to avoid degradation. It will then be necessary to centrifuge the sample immediately upon arrival for 10' at 1500g. A portion of the supernatant will be discarded but the portion of the liquid closest to the bottom will be retained. Given that at the time of performing PL in most patients the positivity or non-positivity for a molecular marker is known, one may proceed in the following ways.

If the patient has a known molecular marker, the pellet will be resuspended in trizol for preservation and RNA extraction. If, on the other hand, the patient does not have a known molecular marker, the pellet will be stored at -20°C.

The ancillary study will be performed by the standardized molecular biology laboratories that will be involved in the study (Rome-Policlinico Tor Vergata, Rome-Policlinico Umberto I, Bologna-Istituto Seragnoli, Bergamo- Giovanni XIII Hospital, Palermo-Ospedali Riuniti)

5.2 Data collection sheet.

Cases will be documented using data collection sheets. A sequential identification number will be assigned to each patient registered in the study. This number will identify the patient and will be included in the data collection sheet thus allowing the patient's anonymity to be maintained. Variables collected will be age, gender, date of ALS diagnosis, immunophenotype at onset, genetic and cytogenetic features of ALS, stratification by risk group, extramedullary localizations, type of chemotherapy, date of first PL, white blood cells at onset and at the time of PL, lactic dehydrogenase levels at onset and at the time of PL, CRL cell count, CRL protein count, CRL cytopsin outcome, date of complete remission. Subsequent data collection sheets will be provided for patient follow-up, at 12 and 24 months after enrollment, in which the number of PLs performed, MMR evaluation, MMR assessment, outcome, date of any recurrence, any SNC radiotherapy, salvage chemotherapy, date of last follow-up, date of death will be reported.

5.3 Statistical considerations.

Patient characteristics will be described by frequency tables for qualitative variables and position indicators for quantitative variables. Associations of clinical-biological parameters with CNS location will be analyzed by Chi-square or Fisher's exact test for qualitative variables and Wilcoxon or Kruskal-Wallis test for quantitative variables. OS will be calculated from the date of treatment initiation to the date of death from any cause; subjects alive at the last follow-up will be censored. DFS will be calculated from the date of achieving complete remission to the date of relapse or death from any cause; subjects alive without progression at last follow-up will be censored. CIR will be estimated via nonparametric method considering death as competitive risk. OS and DFS probabilities will be estimated by Kaplan Meier method; log rank test will be used to compare subgroups. Confidence intervals will be calculated at 95%, all tests will be two-tailed, and differences with $p < 0.05$ will be considered statistically significant. R software (A language and environment for statistical computing. R Foundation for Statistical Computing, Vienna, Austria. URL <https://www.R-project.org/>).

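### Does leaving the CSF flow cytometry result off the section 5.2 variable list endanger the primary endpoint?

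*Combined protocol and SAP*

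**What the plan says.** Section 3.1.1 sets the primary objective: "To assess the incidence of occult CNS localization in adult patients with ALL". Section 2.0 gives the measurement plan: "CSF samples will be studied by investigation of CC and FCM at the time of the first and subsequent diagnostic PLs".

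Two rules classify patients. Section 5.1.1 covers overt disease: "Manifest CNS localization will be defined in the unequivocal presence of leukemic cells in the CSF and/or a mononuclear cell count" of at least 5. Section 5.1.2 calls FCM positive when there are at least 10 clustered events with a leukemic phenotype, and adds: "FCM acquisition will be done locally, but 3 independent, experienced operators will review each case".

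Section 5.2 describes the data sheet. The list begins "Variables collected will be age, gender, date of ALS diagnosis, immunophenotype at onset", and its CSF items appear in "CRL cell count, CRL protein count, CRL cytopsin outcome, date of complete remission" (CRL is used for CSF, as in the background). The 12- and 24-month sheets are ones "in which the number of PLs performed, MMR evaluation, MMR assessment, outcome, date of any recurrence" and further outcomes are reported.

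Secondary objective c is: "Determine the status of CNS occult localization also by molecular biology, comparing the results with those of FCM".

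**The concern.** The list in 5.2 reads as closed, with no wording to show that it only gives examples. It is detailed enough to include CSF protein and lactate dehydrogenase at two time points, yet it omits the one result that decides who counts in the primary numerator. Two listed fields come near it, immunophenotype at onset and extramedullary localizations, but neither is identified as the CSF FCM result.

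Four smaller gaps sit beside it:

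- The CSF count is not specified as mononuclear, although 5.1.1 uses a mononuclear count.
- The follow-up sheets record how many punctures were done, not their results.
- The CSF molecular result is not listed.
- Sections 3 to 5 never state in one sentence how occult disease is built from the two rules.

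If the FCM result really went uncollected, the primary incidence could not be computed. The grouping for survival, relapse and MRD analyses would also be lost, as would the comparator for the molecular objective.

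**Working it through.** **1. The plan's own figure.** Section 4.1.1 asks for a two-sided 95% interval of full width 0.20 around 20% and states a minimum of 70. It does not name the interval method. With the Clopper-Pearson interval the width at 20% is 0.2003 for n = 69 and 0.1989 for n = 70, so 70 is the smallest n that qualifies. At 14/70 the interval is 11.4% to 31.3%. The figure reproduces, and nothing about the variable list touches it.

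**2. What the listed fields could do alone.** The background reports 179 negative, 43 occult and 18 manifest patients: 179 + 43 + 18 = 240. Cytology-negative patients number 179 + 43 = 222, and 222/240 = 92.5%. Carried over to 70 patients as an assumption, that is 70 × 222/240 = 64.75, of whom 70 × 43/240 = 12.5 would be occult. Cytology alone cannot pick those 12.5 out of the 64.75, so the worst case is an incidence known only to lie between 0% and 92.5%.

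**3. Why that worst case is not a realistic size.** It requires that no FCM result be kept anywhere, in a study whose purpose is FCM of the CSF. It also takes only cytology-positive patients as manifest and ignores the listed cell count, whereas 5.1.1 lets the count alone make a patient manifest. The non-manifest share in this study therefore need not be 92.5%.

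**4. Whether the result is otherwise provided for.**

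| Section | What it implies |
|---|---|
| 2.0 | FCM is done on CSF at the first and later diagnostic punctures |
| 5.1.2 | a numerical cut-off, and review of each case by three operators, which should yield an FCM reading per case |
| 5.3 | associations are tested against CNS status, so that status is an analysis variable |
| 3.1.2 c | FCM is the comparator for the molecular result |

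None of these can be carried out without a recorded FCM result for each patient.

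**5. The mononuclear count.** Under 5.1.1 this count separates manifest from non-manifest patients, not occult from negative. A total CSF count below 5 already rules out a mononuclear count of 5 or more, and the total count is listed. Only samples with a higher total and no blasts need the differential, and 5.1.1 already plans cell count and morphology on every sample.

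**6. The occult rule.** Section 5.1.1 defines manifest and 5.1.2 defines FCM positive, so occult is FCM positive and not manifest. The background labels occult as CC-FCM+ in the earlier cohort. The two readings part only for a patient with no blasts, positive FCM and a mononuclear count of at least 5, and only if CC+ meant blasts alone. Each such patient moves the incidence by 1/70 = 1.4 percentage points. The documents do not say how many to expect. The background describes a previous study, so 5.1.1 governs here.

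**7. Later punctures and molecular results.** Section 4.1.1 sizes the study on incidence at diagnosis, so later CC and FCM results do not enter the primary endpoint. No listed objective explicitly analyses them. The molecular work is an ancillary part run in five named laboratories. Its absence from the clinical sheet does not show that its results go unrecorded.

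**The case for a change.** The strongest case for acting is that the omitted item is the primary variable itself. A written list of variables is what centres work from. FCM is acquired locally, so a result without a field might have to be retrieved from each centre afterwards. The remedy would be cheap: a few fields and one sentence, with no new procedure and no effect on the sample size. Fixing the groups in writing before data are seen would also suit a study meant to validate a retrospective finding.

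The textual point stands: no item in 5.2 is identified as the CSF FCM result, and the occult rule has to be assembled from two subsections. The step from there to lost data does not. Section 5.2 is a prose summary in a rough translation (it writes ALS for ALL and mentions MMR twice), so a missing term in it is weak evidence of what the sheet contains. The case review in 5.1.2 also means the FCM result does not rest on local acquisition alone. Low cost by itself does not make this a defect in the design or the analysis.

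**Conclusion.** No change to the plan follows. The CSF FCM result is missing from the list in 5.2, but the sections on design, methods and analysis all require it, and any team carrying them out will record it. The unwritten occult rule is likewise a gap that an analyst fills sensibly from 5.1.1 and 5.1.2. The mononuclear count, later-puncture and molecular fields do not bear on separating occult from negative patients at diagnosis.

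In size, the effect on the required number of patients is nil. The 0% to 92.5% range describes the list read in isolation, not a likely result. The one real ambiguity in grouping is worth 1.4 points per affected patient, with no number of such patients given.

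This rests on two assumptions: that the data sheet itself, which is not among the documents, carries the result that the methods generate; and that 5.1.1 is the operative definition of manifest disease. Some text before the background's group definitions is also missing, so the absence of a written occult rule can be confirmed only for sections 3 to 5.

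### Outcome analyses stop at an unadjusted log-rank test for OS and DFS, with no between-group comparison of CIR, so independence from age cannot be checked

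*Combined protocol and SAP*

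**What the plan says.** - **Outcome analysis (section 5.3).** For the two survival endpoints: "OS and DFS probabilities will be estimated by Kaplan Meier method; log rank test will be used to compare subgroups". For relapse: "CIR will be estimated via nonparametric method considering death as competitive risk". The other tests in 5.3 relate clinical-biological parameters to CNS location one at a time. Tests are two-sided at 0.05, with 95% intervals. No regression model, stratified test, hazard ratio, test of CIR or covariate list appears anywhere in the document.
- **Objectives (section 3.1.2).** Objective a is "To examine associations between occult CNS localization and" OS, DFS, recurrence rates and, as item b4, CIR. The statement of aims before section 2.0 proposes "a multicenter prospective study to evaluate the incidence of occult CNS localization and the impact of such localization on clinical outcome".
- **Background (account of the sponsor's retrospective study).** The multivariable result is given as follows: "status at diagnosis of occult or manifest CNS localization and age over 45 years were found to be independently associated with shorter overall survival". The section closes: "given the heterogeneity of the treatments our patients had received and the long observation period, a prospective validation study is needed to confirm these data".
- **Data (section 5.2).** "Variables collected will be age, gender, date of ALS diagnosis, immunophenotype at onset"; risk group, type of chemotherapy and white cell count are also recorded.

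**The concern.** The study's rationale rests partly on an adjusted result: CNS status still predicted OS once age over 45 was in the model. The new plan has no analysis that can look at this again. If occult patients happen to be older or younger than SNCneg patients, the log-rank comparison mixes the two effects. The association tests in 5.3 could reveal such an imbalance, but the plan has no way to allow for it.

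CIR is a separate gap, and it needs no view on confounding. Objective b4 asks for an association, while 5.3 plans an estimate without saying that it will be made by group and without a test.

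At stake is how the secondary results are read. A p-value without a hazard ratio, from a study sized for incidence, is easily over-read if significant and taken as no effect if not.

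**Working it through.** **1. The plan's own figure.** Section 4.1.1 gives a minimum of 70 for a 95% interval of total width 0.20 at an incidence of 20%. The exact (Clopper-Pearson) width is 0.2003 at n = 69 and 0.1989 at n = 70, so 70 reproduces. It is sized for the incidence interval only.

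**2. Objective against analysis.**
- OS: objective a asks for an association and the background reports an adjusted one; the plan has a crude log-rank test.
- DFS: objective a asks for an association; the plan has a crude log-rank test. The documents show age as prognostic for OS only.
- CIR: b4 asks for an association; the plan has an estimate and no comparison.

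**3. Expected groups at N = 70**, from the retrospective cohort of 240: SNCneg 179/240 × 70 = 52.2; occult 43/240 × 70 = 12.5; manifest 18/240 × 70 = 5.25. At the planning incidence of 20%, occult is 0.20 × 70 = 14. The calculations below use 14 versus 52. With about 5 manifest patients this sums to 71, because the two sources differ slightly.

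**4. What a crude comparison could show when CNS status has no effect.** The documents give no age distribution by CNS status, no age hazard ratio and no event rate, so these inputs are assumed. With proportions p1 (occult) and p0 (SNCneg) over 45 and age hazard ratio h, the initial crude hazard ratio is [1 + p1(h − 1)] / [1 + p0(h − 1)]. For 60% versus 45% and h = 2 this is 1.60/1.45 = 1.103; for h = 3 it is 2.20/1.90 = 1.158. The simulated columns come from 2,000 trials per setting (exponential times, common administrative censoring, about 20 to 40 events, h of 2 to 3).

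| Over 45, occult vs SNCneg | Formula, h = 2 / 3 | Simulated crude HR | Log-rank rejection |
|---|---|---|---|
| 46% vs 46% | 1.00 / 1.00 | 0.97–1.01 | 4–6% |
| 60% vs 45% | 1.10 / 1.16 | 1.09–1.18 | 6–9% |
| 70% vs 40% | 1.21 / 1.33 | 1.21–1.38 | 8–16% |
| 35% vs 50% | 0.90 / 0.85 | 0.84–0.90 | 4–6% |

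The age-adjusted hazard ratio stayed at 0.98–1.02 throughout, with rejection of 4–5%. A separate repeat of the most extreme setting (70% vs 40%, h = 3, 60% events) gave crude 1.38 with 17% rejection, and adjusted 1.03 with 6%.

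**5. Precision.** The factor from the hazard ratio to either 95% limit is exp{1.96 / √[D × (14/66) × (52/66)]}, where D is the number of events.
- D = 20: exp(1.96/1.828) = 2.92.
- D = 40: exp(1.96/2.586) = 2.13.
- With the cohort split instead (43/222 × 179/222 = 0.156), the factors are exp(1.96/√3.12) ≈ 3.0 and exp(1.96/√6.25) ≈ 2.2.

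Schoenfeld power at a true hazard ratio of 2 is 24% at 20 events and 43% at 40. Simulation gave about 30–34% at 20 events, so the formula is somewhat pessimistic there.

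**6. Price and gain of adjusting for age.**
- The standard error rose by 0.3–2.9% over all settings.
- The ordinary two-term Cox fit failed in 0.2–1.7% of trials at about 20 events, 5–11% at about 12, and none at 33–40.
- When a CNS effect exists, adjustment can help even with age balanced. At a true hazard ratio of 2, h = 3 and about 40 events, power was 43% crude and 50% adjusted; the median hazard ratio was 1.83–1.86 crude and 2.05 adjusted. At h = 2 the gain was negligible.

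**7. Gray's test at this size.** With no effect it rejected in 5.3% of trials at 12 relapses and 5.7% at 20. At a cause-specific hazard ratio of 2, power was 22% and 31%.

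**The case against.** The strongest reply is that the plan does what it promises. Objective a says associations, and the aims speak of impact on outcome. Neither promises an age-adjusted effect. The data to be confirmed also include incidence, recurrence and unadjusted survival differences, and the stated reasons for validation are mixed treatments and a long observation period, not age. This stands to a degree: a reader might infer that 5.3 breaks a stated commitment to show independence, and the documents do not support that. What remains is that the adjusted OS finding is among the results put forward for confirmation, and the plan cannot examine it.

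Three further points on that side hold in part.
- The factor reported as independent was occult or manifest status. An occult-versus-SNCneg model alone would fit objective a but not that result, so the pooled contrast is needed as well.
- CIR curves by CNS status with 95% intervals would describe an association. The gap in b4 is the missing grouping and formal comparison, not a complete absence of information.
- The word subgroups, read with objective a, must mean CNS status; what is open is how manifest cases are handled. That alone is missing detail and would not carry the point.

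The small sample is also a fair objection to elaborate modelling. It does not count against one two-term model, and it favours an estimate with an interval over a bare p-value.

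**Conclusion.** The point holds for secondary objective a and should be corrected. Section 5.3 offers only a crude comparison for OS and DFS and none for CIR, although age is collected and the background reports it as an independent OS factor. This rests on the text alone and is secure.

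A reader might go further and infer that the log-rank result will be biased by age. The documents do not support that: no passage links age to CNS status, the direction is unknown, and with balanced age there is no spurious effect. The crude hazard ratios of 0.84 to 1.38 under no CNS effect depend wholly on the assumed imbalance and age hazard ratio.

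Imprecision is a real limit whichever analysis is used. The factors of 2.9 to 2.1 assume 20 to 40 events at the minimum of 70; section 4.1.1 includes all eligible patients over 12 months, so a larger intake would narrow them. The primary incidence objective and its sample size are not affected.

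**What to change.** In section 5.3:
1. State that OS, DFS and CIR are compared between occult (CC-FCM+) and SNCneg (CC-FCM-) patients, in line with objective a.
2. For OS, keep the log-rank test and add one pre-specified Cox model with CNS status and age over 45, reporting unadjusted and adjusted hazard ratios with 95% intervals. Repeat it with occult and manifest pooled against SNCneg, the contrast reported in the background.
3. For CIR, report cumulative incidence by group with 95% intervals and add Gray's test.
4. Label these analyses exploratory.

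The cost is a few sentences and a little R work, with no new data and no change to the sample size. The downside is wide intervals at N = 70, the small rise in standard error shown above, and an occasional failed fit if events are very few. An adjusted DFS model, further covariates (type of chemotherapy, white cell count, risk group) and Firth penalisation for sparse events are optional. Firth fits did not fail in simulation, but with no true effect their median hazard ratio was 1.09 at 20 events and 1.13 at 12, so such results would need to be marked as imprecise.
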